3. STUDY OBJECTIVES

3.1. PRIMARY OBJECTIVE

To determine the placebo-adjusted treatment effect of bexagliflozin tablets, 20 mg on the change in HbA1c from baseline to week 24 in subjects with type 2 diabetes mellitus (T2DM) and inadequate glycemic control.

3.2. KEY SECONDARY OBJECTIVES

The key secondary efficacy objectives of this study are:

- To compare the effect of bexagliflozin to effect of placebo on the change in systolic blood pressure (SBP) from baseline to week 24
- To compare the effect of bexagliflozin to the effect of placebo on the change in body weight from baseline to week 24 in subjects with a BMI ≥ 25 kg/m²

The other exploratory secondary efficacy objectives are:

- To compare the effect of bexagliflozin to the effect of placebo on the proportion of subjects with HbA1c of < 7% over time
- To compare the effect of bexagliflozin to the effect of placebo on change in HbA1c over Time
- To compare the effect of bexagliflozin to the effect of placebo on FPG over time

3.3. SAFETY OBJECTIVES

- To compare the safety of bexagliflozin to the safety of placebo in subjects with T2DM.
- To compare the effect of bexagliflozin to the effect of placebo on the incidence of adverse events (AE) of special interest. AEs of special interest include either upper or lower UTIs, GMI, hepatic toxicity, hypoglycemia, falls and fractures, cardiovascular events, malignancies, hypersensitivity reactions, hypotensive episodes, acid-base disorders, renal failure events, and amputations.
- To contribute major adverse cardiovascular events (MACE+) to an eventual meta-analysis that is intended to exclude a hazard ratio of 1.8 or greater for subjects exposed to bexagliflozin compared to subjects exposed to placebo.

1007728

MACE+ is defined as cardiovascular death, non-fatal myocardial infarction (MI), non-fatal stroke, or hospitalization for unstable angina.

3.4. BRIEF DESCRIPTION

THR-1442-C-450 is a multi-center, randomized, double-blind, placebo-controlled, parallel-group study. It is designed to compare the efficacy and safety of once daily oral administration of bexagliflozin tablets, 20 mg to bexagliflozin tablets, placebo, in treatment-naïve type 2 diabetic subjects or subjects previously treated with no more than one oral hypoglycemic agent (OHA).

All eligible subjects will start a 2 week placebo run-in period. Subjects who miss no more than one dose of the run-in medication, have fasting blood glucose values \geq 250 mg/dL on no more than two consecutive days, and who, at the baseline visit (Visit V5), have an HbA1c level between 7 and 10.5% and a fasting glucose level < 250 mg/dL will be eligible for randomization.

Approximately 210 subjects will be randomly assigned to receive oral bexagliflozin tablets, 20 mg or placebo, in a 2:1 ratio once daily for 24 weeks in an out-patient setting. Subjects with uncontrolled hyperglycemia based on blood glucose levels may receive additional approved anti-diabetic medications. Treatment group assignment at the start of the treatment period will be stratified by HbA1c level at the start of the run-in period (7.0 to 8.5% or 8.6 to 10.5%) and background anti-diabetes treatment status (treatment naïve or not).

Each subject will be contacted by telephone at week 2 (Visit V7) for safety monitoring and will be instructed to return to the clinic at weeks 6, 12, 18, and 24 (Visits V8, V9, V10, V11) for efficacy assessment and safety monitoring. Subjects will return to the clinic for a follow-up visit at week 26 or two weeks after the last dose of investigational product if the subject terminates prior to week 24 (Visit V12).

3.5. SUBJECT SELECTION

The study will enroll both male and female subjects with T2DM. If treatment naïve, they must have an HbA1c at the screening visit of between 7% and 10.5%. Alternatively, prospective subjects may be eligible if at the time of the screening visit they are being treated with one OHA, have an HbA1c of between 6.5% and 10.0% and are willing to complete a 6-week washout. Individuals taking thiazolidinediones are not eligible for the study. A candidate will be considered treatment-naïve if he or she has received no more than 14 days of prescription medication for diabetes in the 12 weeks prior to screening.

1007728

3.5.1. Inclusion Criteria

Refer to protocol section 4.2 for inclusion criteria.

3.5.2. Exclusion Criteria

Refer to protocol section 4.3 for exclusion criteria.

3.6. DETERMINATION OF SAMPLE SIZE

Approximately 210 subjects will be randomized 2:1 to bexagliflozin tablets, 20 mg or bexagliflozin tablets, placebo. The sample size calculation for this study was based on a two group t-test with a two-sided significance test at the 5% level and the following assumptions:

- 1. The difference in mean change from baseline to week 24 in HbA1c in the bexagliflozin group compared to that of the placebo group will be -0.5%.
- 2. The standard deviation for the difference in mean change from baseline to week 24 in HbA1c between the bexagliflozin group and the placebo group will be 1.0%.

Under the above assumptions, an estimated sample size of 128 and 64 evaluable subjects in the bexagliflozin and placebo arms, respectively, yielded a 90% power that bexagliflozin treatment will be found to be significantly different from placebo. To account for an estimated drop-out rate of approximately 10%, the study design anticipates randomizing 140 and 70 subjects in the bexagliflozin and placebo arm, respectively.

3.7. TREATMENT ASSIGNMENT & BLINDING

3.7.1. Treatment Assignment

Eligible subjects who complete the run-in period and meet all study inclusion/exclusion requirements will be randomized in a 2:1 ratio to receive once daily bexagliflozin tablets, 20 mg or bexagliflozin tablets, placebo, during the 24-week treatment period. Subjects will be assigned to treatment groups in sequential order as they qualify for the study, using a centrally located and managed Interactive Web Response System (IWRS). Randomization will be stratified according to HbA1c measured at the last assessment prior to randomization (Visit V5) (HbA1c at 7.0 to 8.5% or 8.6 to 10.5%) and background anti-diabetic treatment status (treatment-naïve or on treatment).

Potential study subjects will be screened and assigned a subject number. Once all screening procedures are completed and the study eligibility is confirmed by the investigator, the randomization numbers will be allocated to subjects within the

1007728

appropriate treatment group by the randomization system. Once a screening or randomization number has been assigned, it will not be re-used in any event. No subjects will be randomized into the study more than once. If a randomization number has been allocated incorrectly, no attempt will be made to remedy the error once study medication has been dispensed. The subject will continue with the randomization number and study medication. The study staff will notify the Sponsor Contact as soon as the error is discovered without disclosing the study medication administered. Admission of subsequent eligible subjects will continue using the next unallocated number in the sequence.

The study will be conducted at multiple investigative sites and will likely involve a variable numbers of subjects at each site. Enrollment will be on a competitive basis but each site will be capped at 21 randomized subjects. However, when a site reaches 21 randomized subjects, if a potential subject at that site is in washout or run in already and wishes to continue with the study, the subject will be allowed to continue and, if eligible, to be randomized. Subject randomization will be deactivated for all sites when the planned number of subjects has been enrolled. However, if a potential subject is in washout or run in already and wishes to continue with the study, the subject will be allowed to continue and, if eligible, to be randomized.

3.7.2. Blinding

This is a double-blind placebo-controlled study. The sponsor, investigators, study coordinators, pharmacists, study subjects, and the cardiovascular endpoint committee (CEC) members will be blinded to the study medication. Upon randomization, each subject will receive a subject randomization number and a drug kit assigned to the subject. To maintain blinding of the individual treatment assignments, central laboratory glucose urinalysis data will not be made available to any study personnel or subjects.

If knowledge of the test substance is needed to manage the subject's condition, the investigator will contact the IWRS to obtain the treatment assignment. If unblinding occurs for any reason, the time and reason for breaking the blind will be recorded in the case report form (CRF) and the sponsor must be notified within 24 hours.

The treatment assignment will continue to be withheld from the CEC members at the conclusion of the study until all global investigational studies are completed and a meta-analysis to assess cardiovascular risk is conducted.

3.8. ADMINISTRATION OF STUDY MEDICATION

The following investigational products will be used for oral administration:

- Bexagliflozin tablets, 20 mg: tablets containing 20 mg of bexagliflozin
- Bexagliflozin tablets, placebo: tablets containing no bexagliflozin

1007728

Bexagliflozin tablets, 20 mg or placebo, should be taken with 250 mL of water in the morning prior to eating or drinking.

Dosing with bexagliflozin tablets, 20 mg or placebo, will be based on randomized assignment. All study subjects will be instructed to self-administer tablets once daily with 250 mL of water in the morning prior to eating or drinking. There will be no change of dose during the 24-week treatment period.

On the day of each scheduled clinic visit, subjects must fast for approximately 10 hours prior to the collection of blood samples. On the day of each scheduled clinic visit, bexagliflozin tablets should be taken with water in the morning prior to eating or drinking (as above) and prior to the collection of blood samples. During the fasting period, only water will be permitted.

3.9. STUDY PROCEDURES AND FLOWCHART

The activities that must be performed at each clinic visit listed below are presented in Table 1.

A visit window of ± 3 days is allowed for all visits except Visit 6. V6 is the day of randomization and the basis for the visit window.

The study staff will contact each subject prior to a scheduled clinic visit to confirm the time of the visit and to remind the subject of proper fasting practice. A subject must be queried to assess compliance with an approximately 10 hours fast prior to blood draw to ensure the FPG and triglycerides values can be accurately determined. If a subject has not fasted for approximately 10 hours, the subject must return as soon as can be arranged (within 1 week) to provide a specimen after proper fasting. Blood samples will be transported to the central lab for analysis.

Statistical Analysis Plan Theracos Sub, LLC

Version 1.2 THR-1442-C-450

Table 1 **Schedule of Events**

Procedure	Screen -ing	Wash	out	Ru	n In	Treatment Period				Follow -Up		
Visit number	V1	V2	V3	V4	V5	V6	V7	V8	V9	V10	V11	V12
Time to Randomization Visit (weeks)	-11	-8	-6	-2	-0.5	0	2	6	12	18	24	26
Informed Consent	X											
Screening or Confirmation for I/E Criteria	X	X			X							
Medical History	X											
Diet and Exercise Counseling		X		X								
Physical Examination					X							X
Abbreviated Physical Examination	X										X	
Vital Signs	X				X			X	X	X	X	X
Electrocardiography	X				X						X	X
Hematology	X				X			X	X	X	X	X
Serum Chemistry and Electrolytes	X				X			X	X	X	X	X
Glycemic Control	X				X			X	X	X	X	X
Serum Lipids	X				X				X		X	X
Urinalysis	X				X			X	X	X	X	X
Infectious Disease Testing	X											
UACR	X				X						X	
Urine Pregnancy Test (all women)	X											
Urine Pregnancy Test (WOCBP)					X			X	X	X	X	X
Diary and Glucometer Dispensation		X		X								
Dispensing Run-in Drug				X								
Diary and Glucometer Record Review			X	X	X	X	X	X	X	X	X	X

Statistical Analysis Plan Theracos Sub, LLC

Version 1.2 THR-1442-C-450

Procedure	Screen -ing	Wash	out	Ru	n In		Т	reatme	ent Perio	od		Follow -Up
Dispensing Investigational Product						X			X			
Adverse Events & DKA Assessments		X	X	X	X	X	X	X	X	X	X	X
Concomitant Medication Assessments		X	X	X	X	X	X	X	X	X	X	X

1007728

4. ENDPOINTS

4.1. PRIMARY EFFICACY ENDPOINT

 Change in HbA1c from baseline to week 24 in subjects with type 2 diabetes mellitus (T2DM) and inadequate glycemic control

4.2. SECONDARY EFFICACY ENDPOINTS

The key secondary efficacy endpoints include:

- Change in SBP from baseline to week 24
- Change in body weight from baseline to week 24 in subjects with a BMI
 ≥ 25 kg/m²

The exploratory secondary efficacy endpoints include:

- Change from baseline in HbA1c over time
- Proportion of subjects with HbA1c of < 7% over time
- Change from baseline FPG over time

4.3. SAFETY ENDPOINTS

- AEs
- AE of special interest
- Clinical laboratory results
- Physical exam results
- Vital signs
- ECG results
- Medication use

1007728

5. ANALYSIS SETS

5.1. SCREENED ANALYSIS SET

The screened analysis set will include all subjects screened for eligibility prior to randomization. The screened population will include screen failures. Unless specified otherwise, this population will be used for subject listings and for summaries of subject disposition.

5.2. SAFETY ANALYSIS SET

All subjects who are randomized and have taken at least one dose of double-blind study medication will be included in the Safety Analysis Set. Safety analyses will be based on the first medication kit that was dispensed to a subject. The Safety Analysis Set is the primary analysis set for safety evaluation.

5.3. INTENTION TO TREAT ANALYSIS SET

All subjects who are randomized will be included in the Intention to Treat (ITT) Analysis Set. All analyses of the ITT Analysis Set will be based on the randomization schedule. The ITT analysis set will serve as the primary set for the efficacy analyses.

5.4. PER PROTOCOL ANALYSIS SET

The Per Protocol (PP) Analysis Set will include all subjects in the ITT who meet the study eligibility requirements and have no major protocol deviations that affect the validity of the efficacy measurements. Detailed protocol deviations that may result in subject exclusion from the PP Analysis Set are described in Section 5.5. The PP analysis set will serve as the secondary set for efficacy assessment.

5.5. PROTOCOL DEVIATIONS

Protocol deviations will be captured during monitoring visits. Major protocol deviations that could affect the primary and secondary variables, in the opinion of the medical monitor, will be considered when determining a subject's eligibility for the PP population.

Table **2** describes some possible types of major protocol deviations. All protocol deviations will be reviewed and determined as major or minor before database lock.

THR-1442-C-450

Table 2 Some Possible Types of Major Protocol Deviations

Category	Criteria	Exclusion			
Inclusion/Exclusion Criteria					
Ineligible subject is enrolled	 Subjects not satisfying HbA1c inclusion criteria Subjects not satisfying eGFR inclusion criteria (inclusion #4 and #7) Treated with SGLT2 within 3 months of screening 	Subject exclusion			
Prior or Concomitant Medication Restrictions					
Use of another SGLT2 inhibitor	Use of an SGLT2 inhibitor as the rescue medication for hyperglycemia	Visit exclusion [exclude data post SGLT2 starts]			
Use of new Diuretic medication	Initiate of new diuretic medication within 12 weeks of randomization	Visit exclusion [exclude data post initiation of a new diuretic]			
Randomization/Blinding					
Unblinding	Blind was broken (requested in IWRS)	Visit exclusion [exclude data post blind broken]			
Dosing Non-Compliance	-Subject missed more than 50% of the investigational product doses between week 12 and week 24	Subject exclusion			

1007728

6. GENERAL ASPECTS FOR STATISTICAL ANALYSIS

6.1. GENERAL METHODS

Statistical methodology and analyses are in accordance with the principles outlined by the ICH E9 guidelines. All statistical analyses will be conducted using SAS statistical software version 9.3 or higher.

Tables, listings and figures (TLFs) will be produced in accordance with the principles outlined by the ICH E3 guidelines. For most summary statistics, data will be analyzed by the following treatment groups: Bexagliflozin 20 mg; Placebo; and total of all treatment groups. All available data from subjects who signed an informed consent will be presented in the subject listings.

Data summaries will use descriptive statistics (number of subjects [n], mean, standard deviation [SD], Q1, median, Q3, minimum and maximum) for continuous variables, and frequency and percentage of subjects for categorical and ordinal variables, unless otherwise specified.

Unless otherwise specified, all statistical tests will be two-tailed using a 0.05 level of significance. All confidence intervals (CIs) will be two-sided 95% CIs.

The analysis visit window will be assigned to data collection. One selected data point per visit will appear in summary tables and figures. Refer to section 6.4 for details. All visit assessment data will be included in shift tables and will appear in the subject listings.

No data imputation will be applied for missing values, unless otherwise specified.

6.2. KEY DEFINITIONS

6.2.1. Baseline Values

For safety endpoints, baseline is defined as the last non-missing value before the first dose of double-blind study medication. For baseline demographics and efficacy endpoints, baseline is defined as the last non-missing value before the randomization date.

6.2.2. First Dose Date

Two "first dose dates" will be required - one for the Run-In period and one for the double-blind treatment period. The first dose date for the Run-In period will be the date of administration of the first dose of single-blind placebo tablets during the Run-In period. The first dose date for the double-blind treatment period will be the date that

1007728

the first dose of randomized, double-blind study drug is administered. Both first dose dates will be obtained from the eCRF. Study analyses will use the double-blind treatment period first dose date.

6.2.3. Study Day

Study Day is the number of days starting from the first administration of double-blind study drug, which is counted as Study Day 1. If the assessment date is after the date of the first double-blind medication, the study day is calculated as date of assessment - date of the first dose administration+1. If the assessment date is prior to the date of the first double-blind medication, the study day is calculated as date of assessment - date of the first dose administration.

6.2.4. Duration

Duration of double-blind treatment will be determined as Double-Blind Duration = Double-Blind Last Dose Date minus Double-Blind First Dose Date plus 1. Duration of Run-In period will be determined as Duration = Last Dose Date in the run-in period minus First Dose Date in the run-in period plus 1.

6.2.5. End of Study

The end of study is defined as the date of final contact as entered on the End of Study page of the eCRF. Any missing date of last contact on the End-of-Study eCRF will be imputed as the date of last contact recorded in the database.

6.3. MISSING DATA

The handling of missing or incomplete data is described for each endpoint and data type (as needed) in Section 7 to 9.

6.4. ANALYSIS VISIT WINDOWS

Table 3 shows how data will be mapped to analysis visits prior to selection of records for analysis. All post-baseline visits, including unscheduled and early termination visits, will be mapped. After mapping the data to the analysis visits, the following rules will apply unless other handling is specified for a particular analysis.

- If multiple records are available within a single analysis visit window, the record closest to the planned assessment day will be selected for analysis.
- If 2 records are equidistant from the target day, then the later record will be selected.
- If a subject has no record in an analysis window, the subject will be considered missing at that visit.

1007728

Table 3 Analysis Visit Windows

Study Day Window	Scheduled day	Scheduled Visit/Week
Day 1 - 63	Day 42	Visit 8/Week 6
Day 64 - 105	Day 84	Visit 9/Week 12
Day 106 - 147	Day 126	Visit 10/Week 18
>= Day 148	Last Dose Date + 1	Visit 11/Week 24

^{*} Week 24 is the end of treatment visit for those subjects completing the study per protocol. For safety endpoint of lab, vital sign, and ECG, the first collection after assigned Week 24 and > 7 days from Week 24 visit will be considered as Week 26 visit.

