3.2.3.3 Main Treatment

During the 24-week treatment period, subjects will be advised to continue daily fasting SMBG measurements. Subjects should contact the clinic if any fasting SMBG is \geq 270 mg/dL (15 mmol/L) from week 1 to week 6, \geq 240 mg/dL (13.3 mmol/L) after week 6 to week 12, or \geq 200 mg/dL (11.1 mmol/L) after week 12 to week 24. Blood glucose values collected via SMBG will be evaluated at study visits by the investigator. In addition, hyperglycemia will be monitored by fasting plasma glucose (FPG) measurement at each study visit.

If hyperglycemia is identified through SMBG or FPG measurements, the investigator will first determine whether the subject had fasted for approximately 10 hour prior to the blood draw to ensure that the FPG value is truly a fasting sample. If proper fasting had not occurred, the subject should be asked to return for a repeat blood test within a week.

During the treatment period, hyperglycemia should be managed first with diet and exercise counseling and should be managed with changes in the medical therapy only if the investigator feels it is necessary for the well-being of the subject (see below, *Prescription of Rescue Medication*). After the treatment period, changes to the medical therapy for hyperglycemia should occur at the discretion of the investigator based on SMBG, FPG, and HbA1c information using local standards of care for subjects with T2DM.

If a concomitant medication for hyperglycemia is to be prescribed, a blood sample must be drawn prior to the administration of the rescue medication so that a final HbA1c value can be determined.

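### SAP 6.4 chooses between a non-fasted FPG sample and its fasted repeat by date alone, and at Weeks 6, 12 and 18 tends to keep the non-fasted one

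*SAP*

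**What the plan says.** SAP 6.4 first assigns records to windows: "All post-baseline visits, including unscheduled and early termination visits, will be mapped". Within a window, "the record closest to the planned assessment day will be selected for analysis", and for ties, "If 2 records are equidistant from the target day, then the later record will be selected". The targets in Table 3 are Days 42, 84 and 126 for Weeks 6, 12 and 18, and "Last Dose Date + 1" for Week 24. SAP 6.4 allows exceptions, since "the following rules will apply unless other handling is specified for a particular analysis". None is given for FPG: SAP 8.2.2.1 specifies the model and no record filter.

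The documents describe two routes to a repeat draw.

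- **Before the draw.** Protocol 3.2.2 requires the fast to be confirmed before blood is taken, and Protocol 7.8 to 7.11 make the draw conditional on it. SAP 3.9 adds that a subject who has not fasted is to come back: "the subject must return as soon as can be arranged (within 1 week) to provide a specimen after proper fasting".
- **After a high reading.** Under Protocol 3.2.3.3 the investigator checks whether a high value came from a fasted subject. "If proper fasting had not occurred, the subject should be asked to return for a repeat blood test within a week".

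**The concern.** The repeat exists to replace a glucose value that does not measure fasting glucose. A selection rule that looks only at the calendar can discard the repeat and analyse the value it was meant to replace. A programmer following the SAP literally would have no basis for doing otherwise.

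The after-draw check in Protocol 3.2.3.3 is set off by hyperglycemia, which is plausibly more common on placebo. If so, non-fasted highs kept in the analysis would fall more often in the placebo arm and make the FPG difference look larger in favor of bexagliflozin. What is at stake is the exploratory FPG analysis over time. The primary HbA1c analysis and the key secondary analyses of SBP and body weight do not use FPG.

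**Working it through.** The documents give no figure for this, so the check enumerates the SAP 6.4 rule.

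**Inputs**

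- Visit offset from target, d = −3 to +3 days (SAP 3.9, visit window).
- Lag from the non-fasted sample to the fasted repeat, r = 1 to 7 days (Protocol 3.2.3.3).
- Closest record wins and a tie goes to the later record (SAP 6.4).
- Equal weight on every d and r. This is an assumption, as the documents give no distribution.

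**Same window?** The latest repeat falls 3 + 7 = 10 days after target. The Week 6, 12 and 18 windows each end 21 days after target (Days 63, 105 and 147), so both records always compete.

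**Rule.** The non-fasted sample is kept if |d| < |d + r|. For d ≥ 0 this always holds. For d < 0 it holds only if r > 2|d|.

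| Visit timing | Lags at which the non-fasted sample is kept | Share |
|---|---|---|
| 3 days early | 7 | 1/7 (14%) |
| 2 days early | 5 to 7 | 3/7 (43%) |
| 1 day early | 3 to 7 | 5/7 (71%) |
| On time, or 1, 2 or 3 days late | 1 to 7 | 7/7 each (100%) |

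Total: 1 + 3 + 5 + 4 × 7 = 37 of 49 = 76%. The fasted repeat is selected in the other 12 of 49 (24%).

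**By lag.** At 1 day and at 2 days the share is 4/7 (57%), and at 3 days 5/7 (71%). Over lags of 1 to 3 days it is (4 + 4 + 5)/21 = 13/21 (62%). At 7 days it is 7/7.

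**Sensitivity to visit timing**

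- If every visit were 1 to 3 days early, the share would be (1 + 3 + 5)/21 = 9/21 (43%), so the tendency reverses.
- SAP 6.2.3 counts the first dose as Day 1. If dosing starts at V6 and visits are timed from V6, nominal Week 6 is Day 43 against a target of Day 42. All offsets move by +1 and the count becomes 3 + 5 + 5 × 7 = 43 of 49 (88%). The latest repeat is then 11 days after target, still inside the window.

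**Week 24.** Put V11 at day 0, with the target one day after the last dose.

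| Last dose | Target | Distance: V11 sample / repeat | V11 sample kept |
|---|---|---|---|
| Day before V11 | 0 | 0 / r | 7/7 |
| Morning of V11 | 1 | 1 / \|r − 1\| | r = 3 to 7: 5/7 |
| Day before the repeat | r | r / 0 | 0/7 |
| Day of the repeat | r + 1 | r + 1 / 1 | 0/7 |

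**The case against.** The strongest objection is that the protocol is built so that the pair should rarely arise. Fasting is confirmed before the draw, and the draw at Weeks 6, 12, 18 and 24 is conditional on it. A subject caught at that check leaves no glucose value behind, so the later fasted sample has no competitor. This stands. The SAP 3.9 instruction to return within a week belongs to that pre-draw check and does not in itself produce two records. The problem is confined to samples found non-fasted afterwards, as in Protocol 3.2.3.3, or drawn contrary to the check. That residue is not empty, because Protocol 3.2.3.3 provides for it, but the documents give no count.

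A reader might infer more than the documents support:

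- **That every required repeat loses to a non-fasted value.** It does not, for the reason just given. Even among pairs the outcome reverses for visits 2 or 3 days early, and Week 24 has no single answer.
- **That the protocol itself declares these values invalid.** It applies that word to calculated LDL-C when triglycerides exceed 400 mg/dL. For glucose it asks for a repeat.
- **That change from baseline routinely sets a non-fasted value against a fasted one.** SAP 6.2.1 says that, for efficacy, "baseline is defined as the last non-missing value before the randomization date", which would favor a later repeat. But the V5 draw is also conditional on fasting (Protocol 7.5), and V5 is only 3 to 5 days before randomization, so a repeat may not fit. The contrast is hypothetical.
- **That lipids are equally exposed.** Appendix 2 of the protocol schedules no lipids at Weeks 6 or 18, and nothing says that a glucose-triggered repeat includes them. Lipids are descriptive safety data, and under SAP 6.1 the shift tables use all visit data.
- **That the bias can be sized in mg/dL.** The documents give neither the frequency of non-fasted samples by arm nor the size of the excess, so any such figure would be invention.

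**Conclusion.** The gap is real but minor. Where a non-fasted FPG value and its fasted repeat both exist at Weeks 6, 12 or 18, the stated rule keeps the non-fasted value more often than not. The 76% depends on even spreads of visit timing and repeat lag; it would be lower with prompt repeats or early visits, and higher with late visits or the one-day shift in study-day counting. At Week 24 the last dose date decides.

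The number of pairs is unknown and probably small. A bias favoring bexagliflozin is plausible but not quantified. FPG is exploratory, with nominal p-values and no multiplicity adjustment (SAP 8.2.2), and no primary or key secondary conclusion depends on it. It is still worth correcting, because here the SAP's rule selects the wrong value rather than merely leaving a detail open.

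**What to change.** Add to SAP 6.4:

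> For FPG, where a window contains both a sample documented as non-fasted and a fasted sample, the fasted sample is selected. The closest-day rule applies among fasted samples. Samples documented as non-fasted are listed but not analysed. The same applies to triglycerides and calculated LDL-C where they were re-drawn.

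The fasted repeat would then be selected in all 49 of the 49 timings above, instead of 12, and at Week 24 whatever the last dose date.

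The cost is a few lines of SAP text and one programming filter, on one condition: fasting status must be available for each draw in an analysable form. The documents say that subjects are asked about fasting, but not that the answer reaches the CRF or the laboratory data, so this should be confirmed before the rule is adopted. There is one small downside: a window holding only a non-fasted sample becomes missing for FPG. HbA1c record selection is unchanged.
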